9.6 Summary of Study Data

For all summaries described in the SAP, the patients enrolled in the ALT-601-201 and randomized to an active dose will be summarized/listed under the heading "NasoVAX", while patients enrolled in Placebo will be summarized/listed under the heading "Placebo".

9.7 Subject Accountability

The screening outcomes will be listed and summarized based on the Consented Population. Consented population in the study will be included in the summary of pre-randomized patient status. The summary will include all patients consented, patients who completed screening, and patients who were screening failure. The reasons for screening failure will also be summarized.

Summaries of analysis populations and patient disposition will be presented by NasoVAX cohort, all NasoVAX cohorts combined, placebo pooled from all cohorts, and overall (all NasoVAX cohorts and pooled placebo) based on the Safety Population and will contain the following information:

- Number of patients who were randomized
- Number and percentage of patients who were dosed (Safety Population)
- Number and percentage of patients who did not receive all doses
- Number and percentage of patients in safety population who completed the study
- Number and percentage of patients who discontinued early and reason for early discontinuation of study

The number and percent of patients in each analysis population will also be tabulated.

A listing will present dates of completion or early withdrawal and the reason for early discontinuation of investigational product treatment and discontinuation of study, respectively, if applicable, for each patient.

The randomization allocation and exclusion from each population will also be listed.

9.8 Subject Demographics and Baseline Characteristics

Demographic and baseline characteristics will be summarized based on the Safety, mITT, and PP populations. Individual patient demographics and baseline characteristics will be presented in listings. Demographic characteristics such as age, sex, race, ethnicity, and BMI, COVID-19 symptoms (Protocol Section 8.2.2), risk factors (Protocol Section 5.3, Exclusion Criterion 5) and baseline resting SpO₂ and pulse rates will be summarized and tabulated by overall NasoVAX cohorts, NasoVAX cohort, and pooled placebo groups. Descriptive statistics will be presented for age and BMI. Frequency counts and percentages will be presented for gender, race, and ethnicity.

ALT-601-201 patient demographic data and baseline characteristics will be summarized descriptively by treatment group and overall for all ALT-601-201 patients (ie, patients on NasoVAX cohort and pooled placebo groups).

A listing of the medical and surgical history will be provided for all randomized patients. Medical and surgery history will be summarized by system organ class (SOC) and preferred term (PT) for each treatment group. Within each level of summarization, patients will be counted only once if they had more than one event reported. Medical and surgery history will be summarized for the Safety Population.

9.9 Analysis of Efficacy Data

Efficacy analyses will be conducted using the mITT and PP Populations with the primary conclusions drawn from the mITT Population. Placebo will be the collective (pooled) across cohorts.

Descriptive statistics will be used to evaluate differences between Baseline and post-Baseline efficacy endpoints. The study is considered exploratory, and inferential statistics will be employed as appropriate.

For the purpose of study efficacy endpoints, resting SpO₂ and resting pulse rate will be assessed on observed data only; if data is missing, it will not be imputed.

The p-values from significance tests will be obtained at a one-sided significance level of 0.025.

No multiplicity adjustments will be made for the efficacy endpoints.

9.9.1 Analysis of Response Data Endpoints

Response data endpoints – the primary endpoint of the proportion of patients with clinical worsening, defined as a 4.0% decrease from Baseline in resting SpO₂ by mobile pulse oximetry on two consecutive measurements during home follow-up, or hospitalization and the secondary endpoint of the proportions of patients requiring hospitalization through Day 42 according to maximal level of oxygen supplementation – will be tabulated by counts, percentages, and the 95% Clopper-Pearson exact CI of the percentage by overall NasoVAX, NasoVAX cohort, and pooled placebo groups. Differences of 95% CIs will also be presented to compare the proportion of patients of each NasoVAX cohort group to the pooled placebo group. CIs will be calculated in PROC FREQ procedure in SAS using the EXACT binomial-option for the individual dose groups and by the METHOD=SCORE riskdiff-option for the differences in treatment groups. In addition, comparisons of proportions of patients in each NasoVAX group against pooled placebo will be conducted using Fisher's exact test.

The Cochran-Mantel-Haenszel (CMH) test will also be used to compare the proportion of patients with clinical worsening and the proportion of patients requiring hospitalization through Day 42 between NasoVAX cohort and pooled placebo groups, while considering the stratification of age groups and risk factors.

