### **10.3.2 Analysis of Efficacy**

For the primary analysis, the proportion of patients with clinical worsening, defined as a 4.0% decrease from Baseline in resting SpO2 on two successive measurements during home follow-up or hospitalization, will be compared between NasoVAX and placebo groups using the Cochran-Mantel-Haenszel test, while considering the stratification of age groups and risk factors, at a one-sided significance level of 0.025. The same approach will be applied for secondary endpoints that are categorical in nature. Sensitivity analyses will be performed to assess the effect of site on the response to study drug. Linear and logistic regression will be employed to examine the effects of Baseline factors, such as age, sex, medications, and medical co-morbidities on response.

Changes from Baseline in Severity of COVID-19, assessed by average decrease in resting SpO2, average increase in resting pulse rate by outpatient pulse oximetry and COVID-19 symptoms (eDiary) during home follow-up, will be analyzed using a mixed model for repeated measures. The model will include the fixed effects of treatment, week, and treatment-by-visit interaction as well as the continuous, covariate of Baseline level. The model will employ an unstructured within patient covariance matrix and a restricted maximum likelihood estimation method.

A Kaplan-Meier method will be applied to compare changes between treatment groups in resting SpO2 over time.

For the purpose of study efficacy endpoints, resting SpO2 and resting pulse rate will be assessed on observed data only; if data is missing, it will not be imputed.

No multiplicity adjustments will be made for secondary endpoints.

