4.4 Randomization and Treatment Assignments

Following completion of the Screening activities, patients who meet all the inclusion and none of the exclusion criteria will be registered by the Interactive Web Response System (IWRS). Eligible patients will be randomly assigned in a 1:1 ratio to the NasoVAX or placebo group within each cohort. Randomization will proceed in 3 cohorts defined by age and risk factors (Exclusion Criterion 5 in the Protocol) for severe COVID-19. The cohorts will be enrolled in ascending order, with Cohort 1 preceding Cohort 2, and Cohort 2 preceding Cohort 3. Cohort 2 will be stratified by age groups of 35-64 years and 65 years and above, whereas Cohort 3 will be stratified by age groups (ages 35-64 years, ages 65 and above) and co-morbidity (one or more risk factors present, no risk factors present). Patients in Cohorts 2 and 3 will be stratified first, and then randomized 1:1 to NasoVAX or placebo. Enrollment of patients ages 35-49 will not exceed approximate 30% of the randomized population of either treatment arm.

The randomization list will be generated by an independent unblinded statistician.

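### SAP 9.9.1 plans no effect estimate or interval that matches the stratified CMH test, and explicitly names none for all NasoVAX versus all placebo

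*SAP*

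**What the plan says.** Protocol 10.3.2 compares the proportion with clinical worsening between NasoVAX and placebo "using the Cochran-Mantel-Haenszel test, while considering the stratification of age groups and risk factors, at a one-sided significance level of 0.025". Protocol 10.4 lets the SAP add analyses but keeps the primary analysis unchanged. Randomization uses the same factors. SAP 4.4 stratifies Cohort 2 by age and Cohort 3 by age and risk factor: "Patients in Cohorts 2 and 3 will be stratified first, and then randomized 1:1 to NasoVAX or placebo".

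For the two binary endpoints, clinical worsening and hospitalization, SAP 9.9.1 plans the following:

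- An exact interval for each group's percentage.
- An interval for differences: "Differences of 95% CIs will also be presented to compare the proportion of patients of each NasoVAX cohort group to the pooled placebo group". The method is the "METHOD=SCORE riskdiff-option for the differences in treatment groups". Strata, weights and a common risk difference are not mentioned.
- Fisher's exact test, also unstratified: "comparisons of proportions of patients in each NasoVAX group against pooled placebo will be conducted using Fisher's exact test".
- The stratified test, listed as an addition: "The Cochran-Mantel-Haenszel (CMH) test will also be used to compare the proportion of patients with clinical worsening", and likewise for hospitalization, "while considering the stratification of age groups and risk factors". No estimate or interval goes with it, and its contrast is again worded as NasoVAX cohort against pooled placebo.

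SAP 9.9 fixes the level: "The p-values from significance tests will be obtained at a one-sided significance level of 0.025". That corresponds to a two-sided 95% interval.

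Elsewhere, SAP 9.9.3 plans Kaplan-Meier estimates and log-rank tests but no hazard ratio. SAP 9.9.4 plans stratum-adjusted mean differences with 95% intervals, but only for SpO₂ and pulse rate. Protocol 10.3.2 mentions logistic regression on baseline factors without naming an adjusted treatment effect.

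**The concern.** The sample size has no significance basis (Protocol 10.1, SAP 9.4), so the effect estimate and its interval are the main product of the trial. As planned, the primary test uses the strata and the risk-difference interval ignores them, so the two rest on different variances. A report could show a CMH result below 0.025 beside an interval that includes zero, and the plan does not say which leads. The comparison the protocol calls primary, all NasoVAX against all placebo, is not explicitly given a difference at all. The continuous secondary endpoints do get a stratum-adjusted difference, so the primary endpoint is served less well than they are.

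**Working it through.** **Inputs.** There is no planned figure to reproduce: the documents give no event rates, effect size or interval width. They do give arm sizes (10 + 14 + 24 = 48 per arm; 20 + 28 + 48 = 96) and the one-sided level of 0.025. The only rates are the hospitalization stopping thresholds of 15%, 20% and 25% for Cohorts 1 to 3 (SAP 5.1.2), which are at best a rough anchor. Everything else below is assumed:

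- Seven randomization cells, 1:1 in each: 20 (Cohort 1); 20 and 8 (Cohort 2, under 65 and 65 or over); 14, 16, 8 and 10 (Cohort 3: under 65 without and with risk factors, then 65 or over without and with).
- CMH on the four age-by-risk-factor strata.
- Placebo risks as stated, and odds ratios of 0.5 and 0.3.
- The Miettinen-Nurminen score interval, because the SAP does not say which score interval is meant.

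**Step 1: what would match the CMH test.** In stratum k, let the arms be n₁ and n₀, N = n₁ + n₀, pooled proportion p and difference d. The Mantel-Haenszel weight is w = n₁n₀/N. The score variance of d at zero difference is p(1−p) × N/(n₁n₀) × N/(N−1). So w² × variance = n₁n₀p(1−p)/(N−1), which is the CMH variance of that stratum. Hence Σwd/√(Σw² × variance) is the CMH statistic without continuity correction (both came to −1.862 on a test table), and the stratified score interval excludes zero exactly when that test is significant. With exact 1:1 allocation w = N/4, so the common difference equals the crude one. Only the variance then differs.

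**Step 2: excess standard error of the unstratified interval.** With no effect and 1:1 allocation, the ratio of unstratified to true SE is √[p̄(1−p̄) / Σ(N_k/96)p_k(1−p_k)].

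- Flat 20%: numerator and denominator are equal, ratio 1.000.
- 15/20/25% by cohort: p̄ = 20.6/96 = 0.2146; 0.1685/0.1670 = 1.009; ratio 1.005.
- 8–40%, for example 8, 10, 20, 12, 20, 25 and 40% in cell order: p̄ = 16.08/96 = 0.1675; 0.1394/0.1301 = 1.072; ratio 1.035.
- 3–60%, for example 3, 6, 25, 8, 25, 35 and 60%: p̄ = 17.72/96 = 0.1846; 0.1505/0.1194 = 1.261; ratio 1.123.

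**Step 3: conflict between test and interval**, by simulation (200,000 to 300,000 trials per scenario). The last column is the share of CMH-significant trials; the larger figure goes with odds ratio 0.5.

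| Placebo risk across cells | SE too large by | CMH significant, interval includes zero |
|---|---|---|
| flat 20% | 0% | 2–4% |
| 15–25% | about 0.5% | 3–5% |
| 8–40% | 3–4% | 7–12% |
| 3–60% | 11–13% | 19–32% |

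The opposite conflict did not occur in these runs. The steep row depends on how risks are spread over the cells: another spread over 3–60% gave 9–11% and 14–23%.

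**Step 4: a second set of assumptions.** Four strata of 27, 9, 8 and 4 per arm, risk ratio 0.4, 1,500 trials per scenario. CMH was significant with the interval including zero in 1.07% of all trials (flat 20%), 1.80% (15/20/25/25%), 3.53% (5/15/20/40%) and 7.40% (5/30/30/60%). CMH was significant in 39.7%, 39.3%, 25.1% and 42.5%. Dividing gives 2.7%, 4.6%, 14.1% and 17.4% of CMH-significant trials, the same order as Step 3. The opposite conflict appeared once, in the 15/20/25/25% scenario: 0.13% of trials, or 2 of 1,500. With the Newcombe interval, total disagreement rose to 3.3%, 4.6%, 7.1% and 10.7% of all trials, so the score variant matters.

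**Step 5: interval width in the Step 4 setting.** Unstratified over stratified mean width for 48 versus 48 was 0.99 to 1.06 over all scenarios, at risk ratios 1 and 0.4. It exceeded 1.02 only for 5/30/30/60% with no effect (0.316/0.299 = 1.06).

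**The case against.** The strongest reply is that this is a reporting choice with little consequence. A crude risk difference is a legitimate description of the marginal effect, the study is exploratory, and any error is on the safe side. Under no effect the unstratified interval excludes zero for benefit in about 1.9% (8–40%) or 1.2% (3–60%) of trials, against 2.4% for CMH, so false positives are not inflated. The larger figures also need gradients that no document supports. The stopping thresholds point to a mild one, although they are not expected rates and the endpoint also counts SpO₂ falls. Even a flat risk gives 2–4% conflict, so not all of it is between-stratum risk counted as noise. All of this stands, and it limits the severity.

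It can also be said that the score clause refers to treatment groups in general and that the tabulation includes overall NasoVAX, so a programmer may well produce the overall interval. That is possible, but the sentence introducing the differences names only the cohort contrasts.

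Two stronger readings are tempting and are not supported:

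- A reader might infer that this is the only treatment-difference interval in the SAP. It is not: SAP 9.9.4 plans adjusted differences for the continuous endpoints.
- A reader might infer that the planned error bars are generally too wide. For the overall contrast the mean width changes by −1% to +6%. For the contrasts the SAP names, the unstratified interval is mostly narrower than a stratified one (ratio 0.89–0.98 in Cohort 1, 0.93–0.98 in Cohort 2, 0.95–1.01 in Cohort 3). It is also off-centre with no true effect when risk varies between strata: by −2.9 to −14.5 points in Cohort 1 and +2.6 to +7.6 in Cohort 3. That comes mainly from comparing one cohort with placebo pooled over cohorts of different risk, which is a separate issue.

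**Conclusion.** The point holds for the binary endpoints. The primary test and the randomization are stratified, the only planned difference interval is not, and no effect estimate is explicitly named for the protocol's primary comparison. This rests on the documents alone.

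The size rests on assumed stratum sizes, placebo risks and odds ratios, and on reading the score interval as Miettinen-Nurminen. If the unstratified interval is applied to the overall comparison, the cost is negligible under a flat or mild gradient, noticeable at 8–40%, and material only if risk runs as steeply as 3–60%. The conflict is almost always a significant CMH test beside an interval that includes zero. Severity is modest: the study is exploratory and the error is conservative. The change is still worth making because it closes a gap at almost no cost.

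**What to change.** In SAP 9.9.1, make the primary effect estimate the Mantel-Haenszel-weighted common risk difference, all NasoVAX minus all placebo, with a stratified score 95% interval. Use the same age-by-risk-factor strata as the CMH test, and run that test without continuity correction so that test and interval agree at zero. State that this CMH comparison is the primary test, as Protocol 10.3.2 has it, and not an addition. Do the same for the proportion hospitalized through Day 42. Keep the unstratified score interval as descriptive, and say which score interval it is.

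The cost is about one SAP sentence and a few lines of PROC FREQ code. No new data are needed, and the strata are already recorded for randomization.

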#### **10.4 Statistical Analysis Plan (SAP)**

The SAP will be developed and finalized prior to the database lock and unblinding of treatment assignment. This plan will confirm the analysis sets used in the analysis, outline all data handling conventions, and specify all statistical methods to be used for all safety and efficacy analyses. The SAP will supersede the protocol with respect to analyses specified, although the primary analysis will remain the same. It is only anticipated that additional analyses may be desired to be pre-specified in the SAP.

---

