9.9.2 Analysis of Continuous Data Endpoints

The continuous data endpoints – the secondary endpoints of average decrease in resting SpO₂ from Baseline and average increase in resting pulse rate from Baseline during the 14 days of home follow-up or hospitalization – will be tabulated by mean changes on each post-treatment day from baseline and their 95% CIs by NasoVAX cohort, pooled placebo, and overall NasoVAX groups. The p-values from parametric (ie, Pearson's t-test) or nonparametric (ie, Mann-Whitney test) tests will be calculated to see significant differences in continuous endpoints between each NasoVAX cohort and pooled placebo groups and between overall NasoVAX and pooled placebo groups.

Changes from Baseline in Severity of COVID-19, assessed by average decrease in resting SpO₂, average increase in resting pulse rate by outpatient pulse oximetry and COVID-19 symptoms (eDiary) during home follow-up, will also be analyzed using mixed model for repeated measures (MMRM). The MMRM model will include the fixed effects of treatment, days, and treatment-by-visit interaction, and the stratification factors (ages 35-64 years vs. ages 65 years and above, one or more risk factors present vs. no risk factors present). The model will also include the baseline characteristics (gender, race) and the corresponding baseline measures (resting SpO₂ at Baseline, resting pulse rate at Baseline). The model will employ an unstructured within patient covariance matrix and a restricted maximum likelihood estimation method.

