Analysis of covariance (ANCOVA) will be used in the analysis of the secondary efficacy endpoints at each post-baseline visit, with the average decrease in resting SpO₂ from Baseline or the average increase in resting pulse rate from Baseline as a dependent variable, treatment arm as a factor, the stratification factors (ages 35-64 years vs. ages 65 years and above, one or more risk factors present vs. no risk factors present) and the corresponding baseline characteristics and measures (gender, race, resting SpO₂ at Baseline or resting pulse rate at Baseline) as covariates. This model will be generated using SAS PROC MIXED with treatment arm in the CLASS statement and visit/day in the BY statement. Comparisons of post-baseline average decrease in resting SpO₂ and average increase in resting pulse rate will be conducted for each NasoVAX dose group against the pooled placebo group. Least square (LS) means and 95% CIs of the LS means of treatment arm, difference of LS means and 95% CIs of the difference in LS means will be obtained from the model via ESTIMATE statements.

9.9.5 *Sensitivity and Post-Hoc Exploratory Analyses*

Sensitivity analyses may be performed to assess the effect of site on the response to study drug. Exploratory analyses of the efficacy data that are not identified in this SAP may also be conducted.

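### The SAP compares each NasoVAX cohort with placebo pooled over all three cohorts, so cohort differences in age and risk are read as treatment effects

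*SAP*

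**What the plan says.** SAP 4.4 has patients "randomly assigned in a 1:1 ratio to the NasoVAX or placebo group within each cohort". SAP Table 1 gives 10, 14 and 24 placebo patients in Cohorts 1, 2 and 3, equal numbers on NasoVAX, and the same NasoVAX dose in every cohort. Each cohort therefore has its own concurrent randomized control.

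SAP 9.9 then sets the efficacy comparator: "Placebo will be the collective (pooled) across cohorts". The later sections apply it cohort by cohort:

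- **9.9.1, response endpoints:** risk-difference intervals for each NasoVAX cohort against pooled placebo; "comparisons of proportions of patients in each NasoVAX group against pooled placebo will be conducted using" Fisher's exact test; and a CMH test "between NasoVAX cohort and pooled placebo groups, while considering the stratification of age groups and risk factors".
- **9.9.2, continuous endpoints:** t or Mann-Whitney tests "between each NasoVAX cohort and pooled placebo groups and between overall NasoVAX and pooled placebo groups".
- **9.9.3, time to event:** Kaplan-Meier curves for each NasoVAX cohort and pooled placebo. Log-rank p-values for the same contrast are optional.
- **9.9.4, ANCOVA:** comparisons "will be conducted for each NasoVAX dose group against the pooled placebo group".
- **9.10 and 9.10.2:** safety summaries in columns for overall NasoVAX, NasoVAX cohort and pooled placebo, and symptom tests of each cohort against the pool.

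No test of a NasoVAX cohort against its own placebo patients is specified.

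The protocol's primary analysis (10.3.2) is one CMH test of NasoVAX against placebo, stratified by age group and risk factors. Protocol 10.4 adds: "The SAP will supersede the protocol with respect to analyses specified, although the primary analysis will remain the same". SAP 9.13 gives the SAP precedence in any conflict.

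**The concern.** Pooling placebo is sensible when cohorts are dose levels drawn from one population. Here the dose is constant and the population changes. Protocol 4.3 says the cohorts are ordered by increasing age and risk of complications. Cohort 1 is the youngest group without risk factors, Cohort 3 allows any adult age and risk factors, and half of the placebo pool (24 of 48) comes from Cohort 3. Sequential enrollment adds a difference in calendar time. The SAP's references to dose groups in 9.9.1 and 9.9.4 do not fit this design.

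Setting Cohort 1 NasoVAX against this pool compares low-risk patients with a mostly higher-risk group. For Cohort 3 the imbalance runs the other way. An apparent gradient from benefit to harm could follow from the design alone and be read as harm in high-risk patients, while a real benefit there could be hidden.

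The primary analysis is also exposed. Read literally, the SAP's CMH sentence turns one randomized test into three non-randomized ones, each at one-sided 0.025 with no multiplicity adjustment.

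**Working it through.** **Inputs from the documents.** Patients per arm are 10, 14 and 24 (SAP 4.1 and Table 1). Total: 2 × (10 + 14 + 24) = 96, which matches the plan. The significance level is one-sided 0.025 (SAP 9.9). No event rates or power are given, so every rate below is an assumption. The 15/20/25% set borrows the hospitalization halt thresholds (SAP 5.1.2) as a convenient gradient; they are not expected rates.

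**Step 1: built-in difference with no drug effect.** For cohort rates p1, p2, p3:

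pooled placebo rate = (10·p1 + 14·p2 + 24·p3)/48; built-in difference in cohort c = p_c − pooled rate.

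At 15/20/25%: (1.5 + 2.8 + 6.0)/48 = 10.3/48 = 21.5%, giving -6.5, -1.5 and +3.5 points. At 5/10/30%: (0.5 + 1.4 + 7.2)/48 = 9.1/48 = 19.0%, giving -14.0, -9.0 and +11.0 points.

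**Step 2: false signals from Fisher's test, no drug effect.** These come from exact enumeration of the cohort's binomial count against the pooled placebo count (the sum of three binomials).

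| Assumed rates, Cohorts 1/2/3 | Built-in difference, points | False benefit, Cohort 1 | False benefit, Cohort 2 | False harm, Cohort 3 |
|---|---|---|---|---|
| 21.5% in all | 0 / 0 / 0 | 0.2% | 0.8% | 1.3% |
| 15/20/25% | -6.5 / -1.5 / +3.5 | 0.4% | 1.0% | 3.1% |
| 5/10/30% | -14.0 / -9.0 / +11.0 | 0.2% | 2.3% | 11.9% |
| 5/15/35% | -17.9 / -7.9 / +12.1 | 1.6% | 3.1% | 12.8% |
| 5/20/50% | -26.9 / -11.9 / +18.1 | 20.4% | 6.0% | 22.8% |

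**Step 3: continuous endpoints.** For the pooled-variance t-test at one-sided 2.5%, simulated with n = 10, 14 or 24 against 48, let the cohort means rise by 0.25 SD per step (0.5 SD in brackets). NasoVAX is falsely favoured in Cohort 1 in 14% (40%) of trials and falsely looks harmful in Cohort 3 in 10% (25%).

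**Step 4: masking of a real effect.** At 5/15/35%, suppose NasoVAX halves the Cohort 3 rate to 17.5%. The true difference is -17.5 points. Against the pool it appears as 17.5 − 22.9 = -5.4 points.

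**Step 5: what stratification leaves.** Cohort 1 lies wholly in the stratum under 65 without risk factors, which also holds patients aged 50-64 from later cohorts. Assume the placebo side of that stratum has 10 Cohort 1 patients at 5% and 16 patients aged 50-64 at 15%. Its rate is (0.5 + 2.4)/26 = 11.2%, so the residual bias for Cohort 1 is -6.2 points. With assumed rates of 25% in the remaining under-65 or no-risk-factor placebo groups (16 patients) and 40% in those aged 65 or above with risk factors (6 patients), the whole pool is at (0.5 + 2.4 + 4.0 + 2.4)/48 = 19.4%, so the unadjusted bias is -14.4 points. Two other assumed mixes leave about -3 points from unadjusted biases of about -8 and -10. Calendar time remains uncontrolled.

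**Step 6: the alternative.** Against own-cohort placebo (10 v 10, 14 v 14, 24 v 24) the expected difference under no effect is zero, and Fisher's one-sided error was at most 1.5% in every scenario tried. The overall 48 v 48 comparison is also unbiased, with error of 0.8% to 1.4%.

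**The case against.** Several points on the other side are sound.

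- **The overall comparison is not affected by pooling.** Allocation is 1:1 within cohort, so overall NasoVAX against all placebo is fair, and SAP 9.9.2 and 9.9.3 include it. The problem is confined to cohort-level contrasts and to the CMH wording.
- **Fisher's test is conservative at these sizes.** At 15/20/25% and 5/10/30% there is no excess false benefit in Cohorts 1 or 2, and false harm in Cohort 3 at 15/20/25% is 3.1%, barely above nominal. The excess depends on a steep gradient.
- **Steep gradients have no documentary support.** Only 40% of Cohort 3 need be 65 or above or have a risk factor. At that minimum, with the remaining 60% at 10%, a 30% cohort rate requires (0.30 − 0.6 × 0.10)/0.4 = 60% in the enriched group.
- **The direction of the one-sided test is not stated.** A test aimed at benefit cannot declare harm, although the interval can still mislead.
- **Stratified analyses remove part of the bias**, and the halting rules work on each treatment group within its own cohort.

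These points limit how often a false significant result would occur. They do not remove the bias in the estimates, which is present whenever risk differs by cohort. The general statement in SAP 9.1 on presenting results by treatment group across cohorts could be read as allowing own-cohort placebo summaries, but the specific sections list only overall NasoVAX, NasoVAX cohort and pooled placebo. The phrase NasoVAX cohort in the CMH sentence may be loose drafting. With SAP 9.13 giving the SAP precedence, it still needs correcting. The exploratory label does not help, because an exploratory trial is read through its estimates.

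**Conclusion.** The concern holds. The cohort-level comparisons in SAP 9.9.1 to 9.9.4 and 9.10.2, and the cohort columns in 9.10, set NasoVAX patients against a control group that was not randomized with them. The Fisher tests, risk differences, t/Mann-Whitney tests and symptom tests carry no adjustment. The CMH, ANCOVA and stratified log-rank adjust only in part.

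Under the two gradients taken as the main range (15/20/25% and 5/10/30%), the built-in differences run from -6.5 to -14.0 points in Cohort 1 and from +3.5 to +11.0 points in Cohort 3, with Fisher false harm in Cohort 3 of 3.1% to 11.9%. All of these rest on assumed rates; if the cohorts had equal risk the bias would be zero, but the protocol itself says risk rises. Separately, the SAP's CMH sentence does not state the primary comparison that the protocol says will stay the same. Both should be corrected before unblinding.

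**What to change.** 1. In SAP 9.9.1 to 9.9.4, 9.10 and 9.10.2, replace pooled placebo in every cohort-level comparison with the placebo patients of the same cohort, and add a same-cohort placebo column to the table shells.
2. Use all 48 placebo patients only for the overall NasoVAX comparison.
3. State one primary test: the protocol's CMH of overall NasoVAX against placebo, stratified by cohort and by the randomization strata within cohort. That is 1 + 2 + 4 = 7 strata. Because the protocol names only age groups and risk factors, record the addition of cohort explicitly as following the randomization.
4. Label the Fisher tests and all cohort-level results as descriptive, and remove the references to dose groups.

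The cost is SAP text and table shells; no data collection changes. Cohort-level intervals become wider because the comparators are 10, 14 and 24 patients instead of 48. That is the precision the randomized comparison within each cohort can give. Seven strata among 96 patients will be sparse, and strata lacking one arm or any events add nothing to the CMH statistic.
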